6.3.3 Antiemetic

[figure not shown]
To counteract the known side effects of this amino acid infusion, such as nausea, 8 mg dexamethasone (antiemetic) and as-required ondansetron (8 mg i.v.) will be administered 15 to 30 minutes before the start of the amino acid infusion (unless there are contraindications for these drugs). From adoption of the protocol version (v6.0), investigators are advised, if required, to control symptoms it is allowed to use antiemetic regime as per site's standard of care and to add extra antiemetic medication including short-term steroids (unless there are contraindications for these drugs). Any antiemetic drug administered to the subject must be documented in the eCRF.

6.3.4 *Optional: Loop Diuretic*

To facilitate the renal elimination of the radioactive peptide, 20 mg furosemide i.v. (loop diuretic) can be administered 30 to 60 minutes prior to the administration of the study medication. This is optional and can be decided by the investigator, but must be documented in the eCRF.

6.3.5 *Administration Scheme*

Figure 14 Administration Schedule for Study Treatment and Concomitant Medication

i.v.=intravenous.

0 h=end of infusion.

Antiemetic and loop diuretic are administered if required.

¹⁷⁷Lu-OPS201 infusion takes place over 120 minutes (see Section 6.2.1).

6.3.6 *Prior and Further Concomitant Treatments*

Subjects will be excluded from the study if they have received any other IRPP. Therapy given subsequently to study medication needs to be considered carefully: if radionuclide therapy is used, the prior radiation doses to the normal tissues need to be considered; and any therapy (such as chemotherapy or radionuclide therapy) should not be started until it is clear that the subject has recovered sufficiently from the adverse events associated with study medication.

During the study period other concomitant medications are permitted at the discretion of the investigator. With the exception of the therapeutic use of SSAs (see Section 6.3.1), NET-specific treatments are not allowed until the end of the core study. In case the investigator considers a NET-specific treatment is deemed necessary for the benefit and well-being of the subject, they should withdraw the subject from study treatment and perform the Withdrawal visit as specified in Section 5.

Vitamins, herbal preparations and other nutritional supplements are permitted during this study. Prior medications (up to 28 days prior to the Screening Visit) and all medications (including herbal products) taken until the EOCT or EOAC Visit, whichever occurs last, must be recorded in the subject's eCRF. The only treatments recorded during the Long-term Follow-up period will be further antitumour treatments for NETs. The indication for each drug, generic name, administration form, strength, dose, frequency of dosing, route of administration, start date and, if applicable, stop date should also be recorded in the eCRF. All medications will be encoded according to the Anatomical Therapeutic Chemical/Defined Daily Dose Classification of the European Pharmaceutical Market Research Association.

6.4 Delay of Administration and Withdrawal from Treatment

6.4.1 Part A

If any of the following occur, no further ^{177}Lu -OPS201 treatment will be administered:

- subject withdraws his/her consent to further treatment;
- cumulative kidney dose exceeds 23 Gy;
- cumulative bone marrow dose exceeds 1.5 Gy, as determined by image-based dosimetry;
- absolute neutrophil count $<1.000 \times 10^9/\text{L}$ (i.e. Grade 3 or higher);
- platelets $<50.0 \times 10^9/\text{L}$ (i.e. Grade 3 or higher);
- if one of the following medical conditions occurs (based on CTCAE v5.0 criteria, see [Appendix 4](#)) and does not resolve within 4 weeks (resolved=toxicity Grade 2 or lower and is at the discretion of the investigator):
 - estimated GFR (eGFR) of $<45 \text{ mL}/\text{min}/1.73\text{m}^2$;
 - liver function tests (total bilirubin and aminotransferases) higher than Grade 3 (unless there is treatment-related liver toxicity, in which case the study treatment should be stopped or interrupted to enable recovery when deterioration of the liver function is noted);
 - any other AE above Grade 2, except hair loss.

The investigator can decide at his/her discretion to discontinue the treatment or to reduce the administered radioactivity for further safety reason than those here listed above to prevent a subject from higher grade toxicity.

Before the administration of Cycles 2 and 3 these criteria must be checked. In the event of withdrawal (discontinuation) from treatment only the EW Visit and the Long-term Follow-up will be performed (with the EW Visit, 8 weeks after the last administration of ^{177}Lu -OPS201).

In some cases, absorbed dose to the bone marrow or kidney may be difficult to evaluate. If there is uncertainty about the radiation dose received to critical organs, but without substantial toxicity, the decision to administer additional cycles is left at the investigator's and subject's discretions. The decision may be either to stop the treatment, administer the full dose or a reduced dose depending on the benefit-risk balance for the subject.

In the situation of persisting Grade 3 and higher bone marrow toxicity a bone marrow aspirate can be considered if at the discretion of the investigator this could contribute to the evaluation of the event.

6.4.2 Part B

If any of the following occur, no further ^{177}Lu -OPS201 treatment will be administered:

- subject withdraws his/her consent to further treatment;
- cumulative kidney dose exceeds 23 Gy;
- cumulative bone marrow dose exceeds 1.5 Gy, as determined by image-based dosimetry;
- platelets $<50.0 \times 10^9/\text{L}$ (i.e. Grade 3 or higher);
- if one of the following medical conditions occurs (based on CTCAE v5.0 criteria, see [Appendix 4](#)) and does not resolve within 4 weeks (resolved=toxicity Grade 1 or recovered, and is at the discretion of the investigator):
 - eGFR of $<45 \text{ mL}/\text{min}/1.73\text{m}^2$;
 - liver function tests (total bilirubin, aminotransferases, alkaline phosphatase and gamma glutamyl transferase (GGT) higher than Grade 3 (unless there is treatment-

- related liver toxicity, in which case the study treatment should be stopped or interrupted to enable recovery when deterioration of the liver function is noted);
- any other related AE above Grade 2, except hair loss, lymphopenia, nonfebrile neutropenia lasting <4 weeks.

The investigator can decide at his/her discretion to discontinue the treatment or to reduce the administered radioactivity for further safety reason than those here listed above to prevent a subject from higher grade toxicity.

Before the administration of Cycles 2 and 3 these criteria must be checked. In the event of withdrawal (discontinuation) from treatment only the EW Visit and the long-term follow-up will be performed (with the EW Visit, 8 weeks after the last administration of ¹⁷⁷Lu-OPS201). In some cases, absorbed dose to the bone marrow or kidney may be difficult to evaluate. If there is uncertainty about the radiation dose received to critical organs, but without substantial toxicity, the decision to administer additional cycles is based on continuing to meet requirements of the inclusion criteria, the investigator's judgement and subject's discretion and must be discussed with and agreed by the sponsor. The decision may be either to stop the treatment, administer the full dose or a reduced dose depending on the benefit-risk balance for the subject.

In the situation of persisting Grade 3 and higher bone marrow toxicity, a bone marrow aspirate can be considered, at the discretion of the investigator, if this could contribute to the evaluation of the event.

6.5 Treatment of Overdose

Accidental overdosing is highly unlikely as medication will be prepared individually for each subject by a qualified radiopharmacist. In the event of accidental overdosing of radio-labelled product, this may result in increased tissue exposure. The subject should be treated according to acceptable protocols by the investigator. This might include measures to increase excretion (e.g. hydration or diuretics) and preparation for the treatment of damage to critical organs such as the kidney and bone marrow (as kidney failure or myelodysplastic syndrome). There is no specific guidance for overdosing. All procedures must be in accordance with the local Radiation Protection guidelines.

Drug overdose is a reportable "Special Situation" and should be reported in the same format and within the same timelines as a SAE, even if it did not result in an AE.

Overdose is defined as any dose administration where >25% in excess of the correct radioactivity amount is administered whether or not associated with an AE.

For monitoring purposes, any case of overdose must be reported in the eCRF's Safety Section in an expedited manner.

If the pharmacy discovers that an overdose has or may have been administered, they should inform the Study investigator and Study Coordinator.

6.6 Post Study Treatments

Following completion of this study, all treatments and interventions will be at the investigator's discretion according to clinical practice and subjects' needs.

6.7 Procedures for Monitoring Subject Compliance

The investigator will be responsible for monitoring subject compliance. Subjects can be withdrawn from the study at any time if the investigator or the sponsor determines that the subject is not in compliance with the study protocol.

The investigator is obliged to keep sufficient documentation of the delivery, use and destruction or return of unused, used or partially used packages of IRPP. The investigator should maintain records that document adequately that the subjects were administered the doses specified in the protocol and reconcile all IRPP received for the trial.

Records of usage should include the identification of the subject to whom the study treatment was dispensed, the quantity and date of dispensing. Administration compliance will be assessed by the trained staff/nurse performing the injection. The radioactivity should also be recorded before and after administration. In case of incomplete injection of the IRPP, the residual volume left (or the residual radioactivity) in the syringe should be recorded in the eCRF. Any discrepancies must be accounted for on the appropriate forms.

[figure not shown]
7 ASSESSMENT OF EFFICACY

For the timing of assessments in this study, refer to the schedule in Section 5.1.

7.1 Efficacy Endpoints and Evaluations

The efficacy endpoints are presented in Sections 3.2.2.4 and 3.3.1.

CCI

The tumour volume assessment:

- Part A: sstr2 lesions are identified as having visible uptake of ^{177}Lu -IPN01072 on SPECT/CT. Only the lesions monitored in dosimetry are included.
 - Part B: sstr2 lesions are identified by the prestudy sstr2 scan. The lesions that are identified on PET or SPECT by sstr2 scan as measured by CT/MRI scan will be the target lesions CCI
- 

7.2 Methods and Timing of Assessing, Recording, and Analysing Efficacy Data

Methods for assessing efficacy data is described below. Timing of efficacy assessments are discussed in Section 5. Procedures for recording efficacy data are discussed in Section 15.1, and methods of analyses are discussed in Section 11.4.

7.2.1 Contrast Enhanced CT Imaging/MRI

Sites will be provided with a study manual including the submission procedures and the imaging acquisition guidelines. Tumour response assessments will be performed on-site (locally) and off-site (centrally, during the core trial period and additional cycles only). CT/MRI images will be used for the tumour response assessments (RECIST v1.1 and other endpoints). An imaging charter will be prepared detailing the independent read set-up and the read methodology. The imaging charter will also include the methodology for the eligibility read.

Radiological assessments for tumour response will be performed at the Screening Visit, repeated at each cycle of therapy, at the EOCT/EOAC/EW Visit, and every 3 months during the 2-year follow-up period or at any time. Additionally, in the event of biological or clinical signs of disease progression further radiological assessments can be made based upon investigator's judgment.

The screening tumour assessments will include pelvis, chest and abdomen, and will be performed within 1 month before Visit 1 Day 1. If a historic CT/MRI scan is present that is not

older than 1 month at Visit 1 Day 1, this scan can be used. However, the site should ensure that all required anatomies are covered and perform scanning for missing anatomies. Imaging parameters used at screening should remain consistent throughout the study. Follow-up imaging should include chest, pelvis and abdomen. The chest should be included if lesions were present at screening.

For chest/abdomen/pelvic scans, the scan should extend from the lateral ends of the clavicles (to ensure complete coverage of lung apices) down to the lesser trochanters or caudally thereof (to ensure complete coverage of inguinal lymph nodes). For abdomen/pelvic scans, the scan should begin cranially at the right dome of the diaphragm and extend down to the lesser trochanters or caudally thereof (to ensure complete coverage of inguinal lymph nodes). Details for image acquisition and provision for central review will be given in a separate imaging charter.

During the Treatment Period (Core Trial and additional cycles in Part B) and the 2-year long-term follow-up period, ⁶⁸Ga-PET scans can be performed, if deemed necessary by the investigator.

7.2.2 Quality of Life Questionnaire

A Quality of Life Questionnaire, composed of a general questionnaire for oncological subjects (QLQ C30; 28 items with a 4-point scale and two items with a scale from one to seven) and a NET-specific questionnaire (GI.NET21; 20 items with a 4-point scale) in paper-form will be completed at baseline (Visit 1, predose), during treatment at Visits 2 and 3 (predose), and at the EOCT/EOAC/EW Visit. It is important that the investigator does not influence the subject's responses to the questionnaire in any way.

8 ASSESSMENT OF SAFETY

8.1 Adverse Events

Adverse events will be monitored from the time that the subject gives informed consent and throughout the study, and will be elicited by direct, nonleading questioning or by spontaneous reports. Further details for AE reporting can be found in Section 8.1.2.3.

8.1.1 Definition of an Adverse Event

The definition of an AE below follows ICH GCP guidelines (see also ICH Guideline for Clinical Safety Data Management: Definitions and Standards for Expedited Reporting).

Adverse Event (AE): any untoward medical occurrence in a subject or clinical trial subject administered a medicinal product, which does not necessarily have a causal relationship with this treatment. An AE can therefore be any unfavourable and unintended sign (including an abnormal laboratory finding), symptom, or disease temporally associated with the use of a medicinal (investigational) product, whether or not considered related to the medicinal (investigational) product.

By definition, for this study, all AEs are regarded as 'treatment emergent', i.e. not seen before treatment or, if already present before treatment, worsened after start of treatment.

Natural progression or deterioration of NETs including symptoms or malignancy under study will be recorded as part of the efficacy evaluation and should not be recorded as an AE/SAE. Death due to disease progression will be recorded as part of the efficacy evaluation and will not be regarded as an SAE. Neuroendocrine tumour status will be monitored through RECIST v1.1 evaluation and completion of Quality of Life Questionnaires (QLQ C-30 and GINET.21). Signs and symptoms should not be reported as AEs/SAEs if they are clearly related to a relapse or an expected change or progression of NETs (symptoms/malignancy). These signs and symptoms should only be reported as AEs/SAEs (depending on the investigator's judgment) if they are:

- Judged by the investigator to be unusually severe or accelerated NETs or;
- If the investigator considers the deterioration of NETs signs and symptoms to be caused directly by the IRPP or OPS301 if applicable.

If there is any uncertainty about an AE being due solely to the NETs under study, it should be reported as an AE/SAE as appropriate.

Preplanned or elective surgeries or therapies should be recorded in the subject's source documents but are not to be considered AEs unless there was any change to the subject's medical condition during the AE collection period.

All AEs will be assessed and documented in the eCRF by the investigator. Follow-up of the AE, after the last visit of the trial, is required if the AE or its sequelae persist. Follow-up is required until the event or its sequelae resolve or stabilise at a level acceptable to the investigator and the sponsor's clinical monitor or his/her designated representative.

8.1.2 *Categorisation of Adverse Events*

8.1.2.1 *Intensity Classification*

The severity of an event is captured in order to subcategorise events. Severity is not seriousness. A very severe event can be nonserious, and a serious event can be of a mild severity. For this study, the US NCI CTCAE v5.0 should be used for determining an event's severity.

All AEs (including SAEs) are to be accurately recorded on the AE page of the subject's eCRF. Each event will be graded for severity using the classifications of CTCAE v5.0 (see [Appendix 4](#)). For events not addressed in the CTCAE v5.0, classifications the following grading will apply:

- Mild (Grade 1) - Mild; asymptomatic or mild symptoms; clinical or diagnostic observations only; intervention not indicated;
- Moderate (Grade 2) - Moderate; minimal, local or noninvasive intervention indicated; limiting age-appropriate instrumental activity of daily living (ADL);
- Severe (Grade 3) - Severe or medically significant but not immediately life-threatening; hospitalisation or prolongation of hospitalisation indicated; disabling; limiting self-care ADL;
- Life-threatening (Grade 4) - Life-threatening consequences; urgent intervention indicated;
- Death (Grade 5) related to AE.

8.1.2.2 *Causality Classification*

The relationship of an AE to IRPP or OPS301 if applicable, administration will be classified according to the following:

- **Related:** reports including good reasons and sufficient information (e.g. plausible time sequence, dose response relationship, pharmacology, positive dechallenge and/or rechallenge) to assume a causal relationship with IRPP or OPS301 if applicable, administration in the sense that it is plausible, conceivable or likely.
- **Not related:** reports including good reasons and sufficient information (e.g. implausible time sequence and/or attributable to concurrent disease or other drugs) to rule out a causal relationship with IRPP or OPS301 if applicable, administration.

Causal relationship of an AE with regards to both administration of IRPP and OPS301 (for subjects who received OPS301) should be recorded. The relationship of the study treatment to an AE will be determined by the investigator and subsequently reviewed by the sponsor.

8.1.2.3 *Assessment of Expectedness*

The reference safety document used in this trial is the Investigator Brochure (IB).

Expected conduct-related AEs: the use of an indwelling cannula for the purpose of blood sampling and administration of study drug may be accompanied by mild bruising and also, in rare cases, by transient inflammation of the vessel wall. After initial irritation, the presence of an indwelling cannula is usually painless and hardly noticeable. The same applies to single vein punctures for blood sampling.

Subjects may also experience discomfort from lying beneath the camera, e.g. back pain.

Expected adverse reaction related to amino acid solution: nausea and vomiting are adverse reactions commonly reported with the use of cationic amino acid solutions as renal protection method.

Expected adverse drug reactions (ADRs): the definition below follows ICH GCP (see also ICH Guideline for Clinical Safety Data Management: Definitions and Standards for Expedited Reporting).

Adverse drug reaction: in the preapproval clinical experience with a new medicinal product or its new usages, particularly as the therapeutic dose(s) may not be established: all noxious and unintended responses to a medicinal product related to any dose should be considered as ADR. The phrase “responses to a medicinal product” means that a causal relationship between a medicinal product and an AE is at least a reasonable possibility, i.e. the relationship cannot be ruled out.

Regarding marketed medicinal products: a response to a drug which is noxious and unintended and which occurs at doses normally used in man for prophylaxis, diagnosis, or therapy of diseases or for modification of physiological function.

Unexpected ADRs: The sponsor will assess all SAEs whether they are expected or unexpected. An unexpected ADR is defined as any adverse drug experience, the nature, specificity or severity of which is not consistent with the applicable product information (e.g. IB for an unapproved investigational product or Summary of Product Characteristics for an approved product). “Unexpected” as used in this definition refers to an adverse drug experience that has not been previously observed and included in the product information, rather than from the perspective of such experience not being anticipated from the pharmacological properties of the investigational product.

8.1.2.4 *Laboratory Test Abnormalities*

Abnormalities in laboratory test values should only be reported as AEs if any of the following apply:

- They result in a change in IRPP schedule of administration (change in dosage, delay in administration, IRPP discontinuation),
- They require intervention or a diagnosis evaluation to assess the risk to the subject,
- They are considered as clinically significant by the investigator, or the laboratory test abnormality suggests a disease and/or organ toxicity that is new or has worsened from baseline based on sponsor review.

8.1.2.5 *Abnormal Physical Examination Findings*

All abnormalities in physical examinations are to be recorded as AEs. If an abnormal physical examination finding meets any of the criteria for an SAE, it must be reported on an SAE Form.

8.1.2.6 Other Investigation Abnormal Findings

All abnormal vital signs are to be recorded as AEs. Results of 12-lead ECG will be immediately analysed by a cardiologist or qualified investigator, and any clinically relevant findings are also to be recorded as AEs. ECG results will also be reviewed centrally. If an abnormal ECG, or vital sign finding meets any of the criteria for an SAE, it must be reported on an SAE Form.

8.1.3 Adverse Events of Special Interest

An adverse event of special interest (AESI) is one of scientific and medical interest specific to understanding of the IMP and may require close monitoring and rapid communication by the investigator to the sponsor. An AESI may be serious or non-serious. The reporting of AESIs allows ongoing surveillance of these events in order to characterise and understand them in association with the use of this IMP.

AESIs for ¹⁷⁷Lu-OPS201 include events with a potential allergic or immunological mechanism which may require more frequent monitoring and/or supportive interventions. These AESIs are being closely monitored in the clinical studies with ¹⁷⁷Lu-OPS201. If the investigator has any questions regarding an AE being an infusion related reaction (IRR), the investigator should promptly contact the sponsor's clinical monitor or his/her designated representative. All AESIs will be assessed and reported as AEs on the AE page of the eCRF by the investigator and periodically evaluated by the sponsor.

The signs and symptoms of IRR may include:

- vasovagal reaction
- hypotension
- palpitations
- tachycardia
- sweating
- gastrointestinal (nausea or vomiting, metallic taste in mouth, right upper quadrant pain, abdominal cramps or bloating / diarrhoea)
- wheezing

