5.2.3.2 Week 6 (Day 42±5) - Part B only

Safety assessments

- clinical laboratory tests (biochemistry, haematology and urinalysis)

5.2.4 Visit 2

During Visit 2, patient may be hospitalised on Day 1 for 24 hours and up to Day 4. The duration of the hospital stay is left at the discretion of the investigator and will depend on the individual subject and the regulatory requirements at the study site. Later assessments may be performed on an outpatient basis.

5.2.4.1 Visit 2, Day 1 (Week 8 (+2 Weeks or Up to +4 Weeks in Case of AEs which have Not Adequately Recovered))

Safety assessments (predosing results must be checked before ¹⁷⁷Lu-OPS201 administration; can be performed one day before)

- physical examination
- weight
- vital signs and 12-lead ECG
- performance status
- clinical laboratory tests (biochemistry, haematology, and urinalysis)
- serum or urine pregnancy test for women of childbearing potential (not surgically sterile or 2 years postmenopausal).
- AEs/concomitant medications
- control of withdrawal from treatment criteria (see Section 6.4)
- 24-hour ECG (Holter) (to start before amino acid infusion).

Efficacy assessments

- survival
- quality of life questionnaire (QLQ-C30; GI.NET21)
- tumour markers
- CT/MRI (same method as in Screening Visit); +2 weeks or up to +4 weeks in case of AEs

CCI

CCI

Administration of ¹⁷⁷Lu-OPS201

See Section 6.2.

Safety assessments (postdosing)

- vital signs (stop of infusion, 30±5 minutes 60±10 minutes, 4 hours ±10 minutes)
- AEs/concomitant medications.

Dosimetric measurements

- blood sampling before and at stop of infusion at 60±5 minutes, 4 hours ±10 minutes
- whole body imaging at 4 hours ±10 minutes.
- SPECT/CT imaging (Part B only) at 4 hours ±10 minutes.

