6.2.1 Dosage and Administration of Study Medication

At each PRRT cycle, the study medication will be administered after the conduct of a safety examination of the subject. The IRPP (20 mL of ^{177}Lu -OPS201) will be administered once per cycle by an i.v. infusion at a rate of 10 mL/h over 120 minutes. Infusion rate modification (up or down) would be under the investigator's judgement and may be temporarily halted or even further slowed down if the subject does not tolerate the IRPP infusion. The overall infusion duration should not exceed 4 hours.

Prophylaxis may be considered if the subject is thought to be at increased risk of infusion-related reactions as per the site's standard of care (see also Section 6.3.3 and Section 6.3.4). Appropriate treatment should be administered should an infusion-related reaction occur including somatostatin analogues. At any time, if infusion-related reactions are encountered, the infusion should be slowed or interrupted.

There are no fasting conditions, nor food restrictions that should apply when administering ^{177}Lu -OPS201 to the subject.

To protect the kidneys, an amino acid solution is infused with ^{177}Lu -OPS201 (Section 6.3.2). The same venous access for IRPP and amino acid solution administration (see Section 6.3.2) will be used. Infusion should be done into the contra-lateral arm of the PK sampling.

The administered radioactivity and mass dose follow the escalation scheme (see Section 3 and Section 6.2).

Note: The rate of infusion can be adjusted based on recommendations from the DRB.

The same venous access for IRPP and amino acid solution administration (see Section 6.3.2) will be used. Infusion should be done into the contra-lateral arm of the PK sampling.

At any time, if infusion-related reactions are encountered, the infusion should be slowed or interrupted.

Radioactivity evaluation (Part A)

In Part A, a cumulative radioactivity of 13.5 GBq (4.5 GBq/cycle \times three cycles) with a peptide mass dose of 300 μg will be evaluated.

Radioactivity and dose escalation (Part B)

See Table 11 for the peptide mass and radioactivity dosing per cohort. See Section 3.1.3 for the rationale of the cohorts and Section 3.8 for dose escalation.

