All AEs and SAEs occurring during the Screening period and more than 6 months after the last dose of study medication will be listed and flagged as occurring before or after (during period 3) the active phase of the study; however, these will not be defined as TEAEs.

TEAEs will be summarised by study part, cohort (part B only) and overall with the number and percentage of subjects with adverse events classified by primary system organ class and preferred term. The number of occurrences of a TEAE will also be presented. The summary of AEs will also be repeated by time period. A listing of AEs by time period will also be presented.

In addition, summary tables will also be presented for SAEs, TEAEs related to ¹⁷⁷Lu-OPS201, TEAEs related to OPS301, treatment emergent ¹⁷⁷Lu-OPS201 related SAEs, OPS301 related SAEs, TEAEs leading to premature discontinuation of study medication, TEAEs leading to dose delays, TEAEs leading to dose reduction, TEAEs leading to dose interruption, TEAEs per decreasing frequency, TEAEs by associated NCI CTC worst grade and by causality. There will also be a separate summary for Adverse Events of Special Interest (AESI) which will be defined as any TEAE related to ¹⁷⁷Lu-OPS201 which occurs the day of ¹⁷⁷Lu-OPS201 administration (same date as ¹⁷⁷Lu-OPS201 administration and at any cycle).

Summary tables of adverse events will be provided with the number and percentage of subjects with adverse events classified by primary system organ class, preferred term (ordered alphabetically) and associated CTCAE version 5.0 worst grade. In the event of multiple occurrences of the same adverse events being reported by the same subject, the maximum intensity (Grade 5 > Grade 4 > Grade 3 > Grade 2 > Grade 1 > missing > not applicable) and the most serious causality (related > not related) will be chosen.

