5 CHANGES FROM PROTOCOL

Dosimetry sections:

Cumulative absorbed dose to the lesions (Gy) has been added as dosimetry endpoint.

AE section:

AESI definition was updated to “any TEAE related to ¹⁷⁷Lu-OPS201 which occurs the day of ¹⁷⁷Lu-OPS201 administration (same date as ¹⁷⁷Lu-OPS201 administration and at any cycle). “

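### The SAP defines AESIs by calendar date and relatedness, not by the allergic, immunological or infusion-reaction content of Protocol 8.1.3, so from Cycle 2 a related finding made before the infusion can count as an AESI

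*Protocol*

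**What the plan says.** Protocol 8.1.3 describes AESIs for ¹⁷⁷Lu-OPS201 by mechanism. They include "events with a potential allergic or immunological mechanism which may require more frequent monitoring and/or supportive interventions". The same section turns to infusion-related reactions: "The signs and symptoms of IRR may include" introduces a list that runs from vasovagal reaction to wheezing. The section sets no time limit and no relatedness condition.

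SAP 3.2.1.2 plans a separate AESI summary. Among the TEAEs judged to be caused by the study product, it picks out by date alone: an event qualifies if it is one "which occurs the day of ¹⁷⁷Lu-OPS201 administration (same date as ¹⁷⁷Lu-OPS201 administration and at any cycle". This rule has three parts: the event is treatment-emergent, it is related to ¹⁷⁷Lu-OPS201, and its date equals an administration date. The nature of the event plays no part, and neither does the clock time within the day.

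SAP section 5 (Changes from Protocol) discloses this: "AESI definition was updated to" the same wording. It gives no reason.

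The TEAE definition in SAP 3.2.1.2 does use the time of administration and the time of the event, but only relative to the first dose.

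**The concern.** A same-date rule works as a proxy for an infusion reaction only if events on that date come after the infusion. At Cycle 1 the TEAE rule largely secures this. At later cycles nothing does, and Day 1 of each cycle opens with a full safety assessment. Protocol 5.2.4.1, for Visit 2 Day 1, says "predosing results must be checked before" the product is given. It lists examination, vital signs, 12-lead ECG, haematology, biochemistry and urinalysis, and Visit 3 is the same. Any new abnormality found there reflects the period since the previous cycle, yet it carries the date of the coming infusion.

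Protocol 11.4.10 plans AESI incidence as a safety tabulation, and SAP 3.2.1 presents safety tables by cohort. Peptide mass rises from 300 to 1300 µg across cohorts, and the synopsis records that the infusion was lengthened from 30 to 60 minutes to 120 minutes at protocol version 8.0. A reader would naturally use the AESI table to compare reactions across those conditions. As defined, the table can mix carry-over from the previous cycle with reactions to the current infusion.

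**Working it through.** The documents give no AESI figure to reproduce, so the check applies the SAP rule to typical events and compares the result with Protocol 8.1.3.

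**Step 1. Can a predose finding become an AE, be related, and be followed by an infusion on the same date?** Yes.
- Haematology and biochemistry are taken predose at every cycle (Protocol 8.2.1 and 8.2.2).
- Clinically significant laboratory abnormalities are recorded as AEs (8.1.2.4). Physical examination and vital-sign abnormalities are also AEs (8.1.2.5 and 8.1.2.6).
- A cytopenia that does not meet the treatment-stopping criteria in 6.4 does not by itself prevent that day's infusion.
- In Part A, the schedule in SAP Table 2 shows no blood count between Day 29 and the next Day 1, so first detection at the predose sample is plausible. Part B adds Day 42.

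**Step 2. Apply the rule.** Events are taken as related to ¹⁷⁷Lu-OPS201 unless stated.

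| Event | Within Protocol 8.1.3? | AESI under SAP 3.2.1.2? |
|---|---|---|
| Abnormality found predose, Day 1 of Cycle 1 | No | No: it precedes the first dose, so it is not a TEAE unless it later worsens or is reattributed |
| New cytopenia found predose, Day 1 of Cycle 2 to 5 | No | Yes: TEAE, related, same date |
| The same cytopenia, sampled the day before (allowed by the schedule footnotes) | No | No: different date |
| Infusion-type reaction during the infusion or later that date | Yes | Yes |
| Allergic or infusion-type reaction starting after midnight | Yes: no time limit is set | No: it appears only in the general and related TEAE tables |
| Same-date reaction attributed to OPS301 only | Unclear: the section concerns ¹⁷⁷Lu-OPS201 | No: it appears in the OPS301-related table |

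Rows 2 and 3 show that the same clinical event is classified differently according to when a site draws blood.

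**Step 3. Number of opportunities.** Later predose Day 1 assessments per subject = cycles − 1. Three cycles give 3 − 1 = 2. Five cycles, possible only in Part B with both optional cycles, give 5 − 1 = 4. These are ceilings, not expected counts.

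**Step 4. Effect of one misclassified subject on cohort incidence, 1/n.**
- n = 3: 1/3 = 33 percentage points.
- n = 5: 1/5 = 20 points.
- n = 10: 1/10 = 10 points.

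**Step 5. Illustration of the same-date window.** SAP 1.3.3.6 equates 08:00 on Day 2 of Visit 1 with about 18 to 20 hours post-infusion. Assume that timing holds, and that it can be combined with a 120-minute infusion.
- Infusion stops at 08:00 minus 18 to 20 h, that is 12:00 to 14:00 on Day 1.
- Infusion starts 2 h earlier, at 10:00 to 12:00.
- Part of the qualifying date before the infusion starts: 10/24 to 12/24, or 42% to 50%.
- Time after the infusion that still qualifies: 24:00 minus 12:00 to 14:00, or 10 to 12 h. With the same start times and a 4-hour infusion it is 8 to 10 h.

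At Cycles 2 to 5, under this assumption, up to half of the qualifying date precedes the exposure that the table is meant to describe.

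**The case against.** The strongest reply is that the change is open, permitted and minor. SAP section 5 lists it, and Protocol section 11 lets the SAP modify the plan. Protocol 8.1.3 is open-ended and supplies no term list, so the SAP had to find some operational rule. The cytopenia route is narrow: blood counts at several earlier visits in each cycle will often give an earlier onset date, laboratory values become AEs only under stated criteria, and findings that stop or delay treatment leave no same-date infusion. AESIs are not named in the primary endpoint list and enter none of the escalation or stopping rules shown.

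Most of this stands, and it limits the size of the problem. It does not remove it: disclosure makes the rule transparent, but the rule still admits events that precede the infusion.

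Four stronger readings are tempting, and the documents do not support them.
- A reader might infer that next-day or OPS301-attributed reactions disappear from reporting. They do not: SAP 3.2.1.2 also plans tables of all TEAEs, of TEAEs related to ¹⁷⁷Lu-OPS201 and of TEAEs related to OPS301.
- A reader might infer that the AESI table is the sole planned summary of hypersensitivity and infusion reactions. That cannot be verified, because the list of tables in SAP 7.2 is not visible in the public text.
- A reader might infer that leaving out OPS301-only events is itself an error, since Protocol 6.2.1 has both products share an access line: "The same venous access for IRPP and amino acid solution administration". But 8.1.3 speaks of AESIs for ¹⁷⁷Lu-OPS201, and causality is recorded separately for each product (8.1.2.2), so the exclusion can be defended.
- A reader might therefore want every 8.1.3 sign counted regardless of attribution. That would overcorrect. Nausea and vomiting are among those signs, and Protocol 1.3.6.1 and 8.1.2.3 describe them as effects of the amino acid infusion. With no time window, unrelated late events would qualify too.

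**Conclusion.** The point holds in limited form. The two definitions differ in kind, and the SAP version has a specific fault from Cycle 2 on: it can count a related event that preceded the infusion, and whether it does so depends on the sampling date. It also cuts off related allergic or infusion-type reactions at midnight, a limit that Protocol 8.1.3 does not contain; the effect is confined to the AESI table.

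The frequency cannot be derived. A false AESI needs an event that is new, recorded as an AE, judged related and dated on the infusion day. The 20 to 33 points for cohorts of 3 to 5 is the weight of one subject, not an estimate of bias. The conclusion rests on the wording of SAP 3.2.1.2 and Protocol 8.1.3 and on the predose schedule; it does not depend on the clock-time illustration.

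Protocol section 11 requires major modifications of the primary endpoint or its analysis to be reflected in an amendment. The documents do not show that this change is major, so the sponsor should record its view.

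**What to change.** In SAP 3.2.1.2, with matching text and a reason in section 5:

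- (a) Require AESI onset date and time at or after the start of that cycle's ¹⁷⁷Lu-OPS201 infusion. State how missing times are handled, since SAP Appendix 1 (items 4 and 5) expects some to be unavailable.
- (b) Restrict AESIs to a prespecified term list set by the sponsor, or to an investigator flag for allergic or infusion reactions, matching Protocol 8.1.3.
- (c) Replace the same-date cut-off with a stated post-infusion window, its length set by the sponsor.
- (d) Keep the relatedness condition for the main table, and show events attributed only to OPS301 separately.
- (e) Keep the present table of related same-day events as supplementary, under another name and limited to onset after the infusion starts.

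The cost is agreeing a term list (or using a flag) and reprogramming one table. Event and administration times already feed the TEAE derivation, so (a) needs no new kind of data.
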